Four patients with PAD (Age: 66.0 ± 10.9 years; Body Mass: 84.3 ± 17.1 kg) completed pilot testing of initial and maximum claudication distances while walking with and without an AFO. Patients completed a progressive-load treadmill test⁶⁷. During the treadmill test, the patients with PAD walked on a treadmill that started at 0% grade and 0.83m/sec. Every two minutes, the grade was increased by 2% up to a maximum of 15% grade. The first indication of claudication pain was recorded as initial claudication distance, while the total distance the patients could walk on the treadmill before stopping because of pain was the absolute claudication distance⁶⁷. Throughout the test, we asked the patient to confirm the presence or absence of pain to ensure the

correct initial claudication distance was recorded. We counterbalanced the effect of the AFO by having two patients walk first with the AFO, while the other two walked first without the AFO to prevent a fatigue effect. On average, the patients' initial claudication distance was 140.1 ± 72.5 meters while walking without the AFO and 183.5 ± 121.2 meters while walking with the AFO (Figure 9). The average maximum claudication distance was 366.0 ± 118.3 meters without the AFO and 492.3 ± 66.8 meters with the AFO (Figure 10). Thus, the four patients increased the maximum distance walked by about 50 meters just by wearing the AFO. These increases in initial and maximum walking distances are comparable to those seen after pharmacotherapy for six months^{29, 32}.

[figure not shown]

Figure 9. Initial claudication distances improve while walking with an ankle foot orthosis (AFO) compared to walking without an AFO in patients with PAD.

[figure not shown]

Figure 10. Maximum claudication distances are increased in patients with peripheral arterial disease when walking with an ankle foot orthosis (AFO).

Wearing an AFO trends towards redistribution of torque to the hip in patients with PAD. Four patients with PAD (Age: 60.3 ± 7.21 years; Body Mass: 82.6 ± 18.05 kg) were tested while walking overground with and without the AFO. Peak torque was calculated for the ankle at the end of the stance phase and hip extensor torque was calculated from early stance in each condition.

The preliminary results show that the ankle plantarflexor muscles have to contribute less torque to walking while

[figure not shown]

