Approach: We propose to study 50 patients with PAD, measuring walking performance with and without wearing a carbon composite AFO. Patients will wear the AFO on the affected leg(s), so patients with bilateral leg symptoms will wear them on both legs while patients with unilateral disease will wear the AFO on the symptomatic leg only. Walking performance will include measurement of initial and absolute walking distances, and lower extremity torque and power. Energy cost and muscle activity will be tested as potential mechanisms contributing to improvement in walking performance. Conditions will be randomized, with half of the subjects performing the tests without the AFO and the other half starting with the AFO walking conditions. All data will be collected in the Biomechanics Research Building (BRB). All subjects will be consented after reporting to the BRB and the outcomes detailed below will be assessed. The entire process is expected to take 2.5 hours.

Outcomes

- 1) **Initial and absolute walking distances:** Walking distances will be determined with a progressive-load treadmill test⁶⁷ with initial and maximum claudication distances as outcomes. During the treadmill test, patients will walk on a treadmill that starts at 0% grade and 2.0 mph. Every two minutes, the grade will be increased by 2% up to a maximum of 15% grade, and the speed held constant throughout the test⁶⁷.
- 2) **Lower extremity torque and power:** Biomechanical data will be collected using eight in-ground AMTI force platforms and a 12 camera high speed digital motion capture system (Cortex 5.1, Motion Analysis Corp, Santa Rosa, CA) to collect three dimensional kinematics (60 Hz) and kinetics (ground reaction forces, 600 Hz). Reflective markers will be placed at specific anatomical locations on the lower limbs, utilizing the marker systems of Vaughan⁷⁰ and Nigg⁷¹. Following the setup, kinematics and ground reaction forces will be recorded while the subjects walk with their self-selected pace through a ten-meter pathway. Each patient will be tested before the onset of claudication pain (pain free) with a mandatory one-minute rest period between the walking trials to insure that all trials are in a pain free condition. A total of five walking trials per leg will be collected. Following the collection of overground data, the patients with PAD will be allowed to rest.

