- 6) **Quality of Life:** The Walking Impairment Questionnaire⁷⁴, Medical Outcomes Short Form 36, and Edinburgh Claudication Questionnaire will be used to assess quality of life. The Walking Impairment Questionnaire has been validated in patients with claudication⁷⁴ and the Short Form 36 has been extensively evaluated and tested with a variety of populations and is able to distinguish between groups of varying health status^{75, 76}. The Edinburgh Claudication Questionnaire was developed in an iterative, systematic fashion and has been implemented as a more holistic approach to identify presence of intermittent claudication in many clinical trials.^{20, 77-82}
- 7) **Morphometric parameters:** An ultrasound transducer (LS128 CEXT-1Z, Telemed, LT, Lithuania) will be used to assess thickness of the plantarflexor muscles using a standard real time B-mode image. Muscle thickness will be measured on the posterior medial and lateral surfaces, 20, 30, and 40% between the lateral malleolus of fibula and the lateral condyle of the tibia. The average values of muscle thickness at all measured sites will be the primary outcome measure.
- 8) **Muscle Oxygenation:** Continuous-wave near infrared spectroscopy (Moxy Monitor, Fortiori Design LLC, MN, USA) will be measured bilaterally on the gastrocnemius calf muscle before, during and after the walking distance test. We will measure resting StO₂, minimum StO₂ during the maximal treadmill test, time to minimum StO₂, and the StO₂ recovery time.
- 9) **Muscle Strength and Endurance:** An isokinetic dynamometer (Biodex 4 Medical Systems, Inc. USA) will be used to measure peak isokinetic strength (torque) of the ankle and hip of the more symptomatic leg. Peak torque and total work performed for ankle plantarflexion, ankle dorsiflexion, hip flexion, and hip extension will be measured. Subjects will perform one trial of five repetitions at 60 degrees/second to assess strength, and one trial of 15 repetitions at 120 degrees/second to assess endurance.

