Statistical analysis: A portion of patients from Aim 1 will be randomized to one of two intervention arms (control then AFO, or AFO then control). We expect differences from a 3-month training to be larger than the immediate differences shown in Aim 1. A sample size of 30 subjects (15 per treatment arm) will provide 80% power to detect differences of 0.59 standard deviations between walking with and without an AFO, using a paired t-test for sample size estimation purposes only, and a significance level of 0.025 to adjust for multiple testing. This sample size will also allow us to detect an effect size of 1.2 for differences between the two groups at each time point. Assuming a 10% drop-out rate, we will randomize 17 per group, for a total of 34 subjects. For statistical analysis, a linear mixed modeling approach (or generalized linear mixed model, as appropriate) will be used. This approach will allow us to detect differences within and between groups, and adjust for confounding variables. The main comparison of interest will be changes in walking distances due to wearing the AFO. The use of the crossover design will allow us to investigate several questions of interest: 1) If walking distances improve after wearing the AFO for 3-months; 2) If walking distances worsen over the first 3 months for subjects not wearing the AFO in the first period; and 3) If the improvement in walking distances from wearing the AFO for three months is retained over the second 3 months (no AFO). To evaluate the relationship between improvements in walking performance, physical activity, and quality of life, and improvements in morphometric parameters, muscle oxygenation, and muscle strength and endurance, multiple correlations will be used. The level of significance will be set at p=0.05.

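### Time to minimum StO₂ is capped by treadmill test length, which is absolute walking distance, so the planned Aim 2 correlation between the two can arise without any change in oxygenation

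*Combined protocol and SAP*

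**What the plan says.** Specific Aim 2, Outcomes, item 8 (Muscle Oxygenation) has near-infrared spectroscopy "measured bilaterally on the gastrocnemius calf muscle before, during and after the walking distance test". Besides a resting value, the measures are "minimum StO₂ during the maximal treadmill test", how long the patient takes to reach that value, and how long recovery takes.

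The test is defined in Specific Aim 1, Outcomes, item 1, and item 1 of the Aim 2 outcomes refers back to it. It runs "with initial and maximum claudication distances as outcomes". The belt is level at the start and moves at 2.0 mph; on pace the text adds "and the speed held constant throughout the test", while on load its rule reads: "Every two minutes, the grade will be increased by 2% up to a maximum of 15% grade". The account of the pilot treadmill test, earlier in section 4, gives the end point: the distance reached "before stopping because of pain was the absolute claudication distance".

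The Aim 2 Statistical analysis paragraph makes change in walking distance the main comparison. To relate improvements in walking performance, physical activity and quality of life to improvements in the muscle measures, oxygenation included, "multiple correlations will be used", at the 0.05 level. Section 1 states the expected correlation as part of the Aim 2 hypothesis. No StO₂ reading at a fixed time or grade is specified, and no allowance for test duration in these measures.

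**The concern.** One recording supplies both sides of the correlation. At constant speed, absolute distance is test duration in other units. Time to minimum lies inside the test, and if StO₂ falls until the patient stops, it equals the duration. A patient who walks further for any reason has room for a later minimum, so the two changes tend to move together even when the StO₂ curve at each workload is identical at both visits. A positive correlation would then be read as evidence that better oxygenation accompanies better walking, which Aim 2 sets out to show.

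Minimum StO₂ is exposed in a different way. A longer test also reaches steeper grades, so the minimum may be read after more work. That pushes it down and could hide a real improvement. Recovery time may lengthen for the same reason.

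**Working it through.** **Figures in the plan.** The plan gives no figure for these correlations. Its Aim 2 power statement reproduces (paired t-test, n = 30, 0.59 SD, two-sided 0.025: 80.2% against the stated 80%), as do the 34 randomized, but neither bears on this point.

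**Step 1: duration and distance.** 2.0 mph = 0.894 m/s, so duration = distance / 0.894. The pilot mean maximum distances were 366.0 m without and 492.3 m with the AFO:
- 366.0 / 0.894 = 409 s = 6.8 min, in the 6% stage.
- 492.3 / 0.894 = 551 s = 9.2 min, in the 8% stage.

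The second test is 35% longer and one stage steeper. The pilot text also describes the gain as about 50 m. On that figure the test ends at 416 / 0.894 = 465 s = 7.75 min, still in the 6% stage.

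**Step 2: correlation when time to minimum carries no oxygenation information.** Let time to minimum = f × duration, with f drawn independently at each test from a uniform distribution on (a, 1). Let μ = (1 + a)/2 and v = (1 − a)²/12, let D1 and D2 be the two distances, and let σ be the SD of D2 − D1, taken as independent of D1. Then

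r = μσ / √[μ²σ² + v(E D1² + E D2²)].

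Speed cancels. Inputs:
- Mean distances of 366.0 and 492.3 m, from the pilot.
- σ = 126.3 / 1.29 = 97.9 m, back-calculated from the standardized effect in the Aim 1 Statistical analysis.
- Baseline SD of 80 m, assumed.

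E D1² + E D2² = (366² + 80²) + (492.3² + 80² + 97.9²) = 398,700.

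For a = 0: μ²σ² = 0.25 × 9,584 = 2,396; v × 398,700 = 33,225; r = 48.95 / √35,621 = 0.26.

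With σ = 50 m the sum of squares is 391,615. For a = 0: r = 25 / √(625 + 32,635) = 0.14.

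| Range of f | r, σ = 97.9 m | r, σ = 50 m |
|---|---|---|
| 0 to 1 | 0.26 | 0.14 |
| 0.3 to 1 | 0.45 | 0.25 |
| 0.5 to 1 | 0.63 | 0.38 |
| 0.7 to 1 | 0.84 | 0.62 |
| 0.9 to 1 | 0.98 | 0.93 |

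Using the pilot SD of 118.3 m as the baseline spread hardly matters: 0.62, 0.83 and 0.98 for the last three rows at σ = 97.9 m.

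**Step 3: what these values mean with 30 patients.** The critical |r| at two-sided 0.05 is 0.361. With σ = 97.9 m, the chance of a significant correlation from the coupling alone is about 29% for the first row, 70% for the second and above 95% from the third on. With σ = 50 m it is about 11% for the first row and 55% for the third. The nominal rate is 5%.

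**Step 4: a second model, with StO₂ curves.** Each patient's underlying curve was held identical at both visits and only duration changed. Assumptions: exponential fall with time constant 40, 150 or 300 s; further drift of 0 or 1 point per minute; sample noise SD 1.5 points; visit-to-visit SD 3 points; recovery modelled from end-test depth; baseline SD 118 m; change SD 98 m. Correlations with change in absolute distance:

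| Measure | r | Chance of significance, n = 30 |
|---|---|---|
| Time to minimum | 0.37 to 0.96 | 52% to about 100% |
| Minimum StO₂ | −0.06 to −0.53 | 6% to 87% |
| Recovery time | 0.02 to 0.33 | 5% to 42% |
| StO₂ at a fixed early time (about 110 s) | about 0 | 5% |

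The low ends come from an early plateau with no drift.

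**The case against.** The strongest reply is that the size of the effect depends on StO₂ kinetics that the documents do not give. Placing the minimum in the second half of every test yields correlations of 0.63 and above, but that placement is an assumption. If the minimum can fall anywhere, r drops to 0.26, below the critical value. The distance inputs are also fragile: four patients, tested acutely with and without the device rather than over three months. The 97.9 m is close to the root mean square of the two condition SDs, √[(118.3² + 66.8²)/2] = 96.1 m, so it may not be an SD of within-patient change. This stands, and it is why the result is given as a range. It does not remove the cap on time to minimum, which follows from the test design alone.

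A reader might infer that all three exercise measures are compromised alike. The figures do not support that. Only time to minimum is bounded by duration. For minimum StO₂ the link can be close to nil, and it runs against the hypothesis. For recovery time every modelled value lies below 0.361.

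A reader might also infer that Aim 2 as a whole is in doubt. It is not. The main comparison of walking distances does not use StO₂. Resting StO₂ is taken before the walk. Physical activity and quality of life are not measured by the length of this test. Initial claudication distance is at most indirectly affected.

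The planned mixed model, with its adjustment for confounders, is not an answer: the mechanism analysis is by correlations, and duration is the outcome itself.

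**Conclusion.** The point holds for the mechanism correlation between time to minimum StO₂ and absolute walking distance. As planned, that correlation can support the Aim 2 mechanism with oxygenation at a given workload unchanged. The built-in r is about 0.26 to 0.98 with a change SD of about 98 m and about 0.14 to 0.93 with 50 m, against a critical value of 0.361. Where in this range the trial would fall depends on StO₂ kinetics and on the spread of three-month change, and the documents give neither. A spurious correlation is thus possible, and likely if the minimum usually comes late in the test, but it is not certain.

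For minimum StO₂ the bias may run the other way (r about −0.06 to −0.53) and hide a benefit. For recovery time it is smaller and uncertain (0.02 to 0.33). The plan should be changed on this point, but the matter is confined to interpretation of the mechanism and does not touch the main Aim 2 result.

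**What to change.** For the correlations with absolute walking distance, replace the end-test measures by StO₂ at a matched time and grade within patient: the value at the end of the last stage completed in all of that patient's tests, and the StO₂ slope up to that time. If a patient does not complete the first two-minute stage in every test, use a common earlier time.

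Compare only tests done with the same AFO status, and state that status for each follow-up test, which the Aim 2 text does not do. The protocol's premise is that the device lowers the demand on the calf, so equal grade is equal calf load only when AFO status is the same.

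Report time to minimum and minimum StO₂ against absolute distance as descriptive only. Interpret recovery time with the end-test workload stated. Resting StO₂ and the correlations with physical activity and quality of life need no change on this account.

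The cost is reprocessing a continuous signal that the plan already records; no extra visit, device or patient is needed. The downside is that signal after the shortest of a patient's tests is not used in the matched measure.

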AFO and Control Intervention: Patients will be asked to wear an AFO each day for three months. Subjects will have an off-the-shelf AFO (Figure 2) chosen initially based on shoe size and adjusted or exchanged for a different size during the initial evaluation after entering the study. The patients will be asked to wear the AFO at all times except when they are in bed or showering/bathing. The instructions given to the patients about walking will be the same as typically provided by clinicians, which is to walk 30 minutes per day, most days/week. We have chosen this specific AFO device because it is already available for use in a clinical environment, is composed of a carbon-composite material that will capture and return energy during the gait cycle, and has successfully contributed to propulsion during walking in other clinical populations^{26, 28}. Patients will be able to contact the nurse coordinator at any time if they need the AFO adjusted or have questions about what should happen during the intervention. Subjects in the control arm will be asked to continue the same lifestyle for three months. The intervention arm order will be randomized (see Statistical Analysis)

Outcomes: All outcomes will be assessed at baseline and following each arm (control and AFO).

- 1) Initial and absolute walking distances, 2) Lower extremity torque and power, 3) Muscle activity, and 4) Energy cost will all be measured as described for Specific Aim 1.
- 5) **Physical Activity:** Participants will wear the Actigraph (Actigraph GT3X, Actigraph, FL, USA) accelerometer on their hip for seven days (the whole day except when sleeping) prior to starting the AFO intervention to measure baseline activity level. The accelerometer will be mailed back to researchers in a pre-paid envelope. Two weeks prior to the post-intervention visit to the laboratory, an accelerometer will be mailed to participants to wear the final seven days before the visit. Average steps/day, maximum cadence, and average peak activity index will be calculated.

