Expected results/possible limitations: We hypothesize that an AFO intervention will increase walking performance, physical activity levels, and quality of life through improvements in the function of the muscles of the treated legs. If our hypothesis is correct, the AFO intervention is a new effective conservative intervention for patients with PAD. Because the premise is that the AFO will maintain overall torque and power while requiring a lower contribution from the leg muscles of patients, the patients will be able to walk further, placing less stress on their leg muscles, thereby allowing regeneration of structure and function of the muscles. Another possibility is that the patients experience an improvement in their walking performance, physical activity levels and quality of life but do not see improvements in muscular function of the legs. In this case, the

AFO would still be beneficial for patients to use. However, if none of the components of our hypothesis are correct, and neither the function and quality of life nor the muscle characteristics improve despite conscientious use of the AFO, then our study would direct us away from AFO-type treatments and towards other therapies and rehabilitation geared towards muscle health.

Specific Aim 3: Determine the feasibility of a three month AFO intervention

Approach: We will utilize Bowen and colleagues' standards for feasibility studies to measure the feasibility of using an AFO over three months in a random subset of 20 patients from Specific Aim 2. We will employ interviews and surveys throughout the three-month AFO intervention period to assess the following outcomes.

Outcomes

- 1) **Acceptability:** Interviews and a satisfaction survey will be implemented to assess satisfaction of using an AFO, intent to continue use, and perceived appropriateness measured. The research team will conduct interviews at 1.5 months, and three months. Interviews will last no longer than 30 minutes and will take place at the UNO Biomechanics Research Building. Satisfaction surveys for all participants will be completed during the final assessment in the Biomechanics Research Building.

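### Aim 2 is planned at 0.025 for walking distance but analysed at a blanket 0.05 with no outcome hierarchy, and its interpretation text lets improvement in any component avoid the negative conclusion

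*Combined protocol and SAP*

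**What the plan says.** All places are in section 4, Approach.

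- **Main comparison** (Specific Aim 2, Statistical analysis): "The main comparison of interest will be changes in walking distances due to wearing the AFO".
- **Planning level** (same paragraph): "A sample size of 30 subjects (15 per treatment arm) will provide 80% power to detect differences of 0.59 standard deviations", from a paired t-test at "a significance level of 0.025 to adjust for multiple testing".
- **Analysis level** (end of that paragraph, directly after the sentence on correlations): "The level of significance will be set at p=0.05". No adjustment, testing order or exploratory label follows.
- **Other outcomes** (Specific Aim 2, Outcomes, items 5 to 9): for activity, "Average steps/day, maximum cadence, and average peak activity index will be calculated"; for strength and endurance, "Peak torque and total work performed for ankle plantarflexion, ankle dorsiflexion, hip flexion, and hip extension will be measured". There are also three questionnaires, four muscle-oxygenation measures and muscle thickness. Of these five groups, only thickness has a named primary measure.
- **Interpretation** (Specific Aim 2, Expected results/possible limitations): "if none of the components of our hypothesis are correct, and neither the function and quality of life nor the muscle characteristics improve", even though the device is worn as asked, "then our study would direct us away from AFO-type treatments". The same paragraph treats the AFO as still worthwhile if walking performance, activity and quality of life improve together without muscle change.

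**The concern.** The statistical paragraph and the interpretation paragraph do not meet. The first points to walking distance. The second states what a negative Aim 2 would look like and does not tie it to walking distance. If walking distance is flat and one other measure is significant, the negative conclusion is not reached, and nothing says what is concluded instead. *Improve* is not defined, and no measure is named as deciding for activity or quality of life.

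The allowance for multiple testing also appears only in the sample-size calculation. The more outcomes compared at an unadjusted 0.05, the likelier it is that an AFO with no effect produces a favourable result by chance. At stake is how secure the Aim 2 conclusion is, including the separate hypotheses about physical activity and quality of life.

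**Working it through.** **1. The plan's own figure.** Inputs from Specific Aim 2, Statistical analysis: n = 30 pairs, effect 0.59 SD, alpha 0.025. For a two-sided paired t-test, the noncentrality is 0.59 × √30 = 3.23, with 29 degrees of freedom and critical value 2.36. Power is 80.2%, which reproduces the stated 80%. At two-sided 0.05 (critical value 2.05) power would be 87.8%.

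**2. Count of measures.**

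| Outcome group | Where listed | Measures |
|---|---|---|
| Walking distances | Aim 1, Outcomes, item 1 | 2 |
| Physical activity | Aim 2, Outcomes, item 5 | 3 |
| Questionnaires, one score each | item 6 | 3 |
| Muscle thickness | item 7 | 1 |
| Muscle oxygenation, not split by leg | item 8 | 4 |
| Strength and work, 4 movements × 2 | item 9 | 8 |
| **Subtotal** | | **21** |
| Ankle and hip torque and power | Aim 1, Outcomes, item 2 | 4 |
| **Total** | | **25** |

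This leaves out electromyography, energy cost, questionnaire subscales and the remaining gait measures. On the narrower reading, the hypothesis in the interpretation paragraph names four components: walking performance, physical activity, quality of life and muscle function.

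**3. Chance of at least one significant favourable result when the AFO does nothing.** Assumptions: each comparison is tested at two-sided 0.05, so 0.025 in the favourable direction, and test statistics share one common correlation ρ. The documents give neither the sidedness nor ρ.

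For ρ = 0: P = 1 − (1 − 0.025)^k.

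- k = 4: 1 − 0.975^4 = 9.6%
- k = 21: 1 − 0.975^21 = 41.2%
- k = 25: 1 − 0.975^25 = 46.9%

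For ρ > 0: P = 1 − ∫ φ(u) Φ((1.96 − √ρ·u)/√(1 − ρ))^k du, integrated numerically.

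| Tests (k) | ρ = 0 | ρ = 0.5 | ρ = 0.8 |
|---|---|---|---|
| 1 | 2.5% | 2.5% | 2.5% |
| 4 (named components) | 9.6% | 7.8% | 5.7% |
| 21 | 41.2% | 21.6% | 11.4% |
| 25 | 46.9% | 23.4% | 12.1% |

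**4. Two walking distances at the planned level.** With each at two-sided 0.025, the favourable tail is 0.0125. At ρ = 0 the rate is 1 − (1 − 0.0125)² = 2.5%; at ρ = 0.8 it is 2.0%. Tested at 0.05 each, the two distances would give 4.9% and 3.9%.

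**5. Cost of making walking distance the sole ground for abandonment.** At alpha 0.025 and n = 30, power is 80% at 0.59 SD and 59% at 0.47 SD, the pilot effect used to plan Aim 1. An effective AFO would then be dropped in about 20% and 41% of trials respectively.

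**The case against.** The interpretation paragraph is narrative about expected results, not a formal decision rule. Nothing in it displaces walking distance as the main comparison. Its favourable scenarios are conjunctive: the hypothesis as a whole is correct, or walking performance, activity and quality of life all improve. One chance result on maximum cadence or dorsiflexion work satisfies neither. That mixed case is simply not addressed. All of this stands.

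A reader might infer that the plan tests every measure at 0.05. The documents do not say so measure by measure; it is a reading of one general sentence. The Aim 2 Approach also presents thickness, oxygenation and strength/endurance as ways to investigate mechanisms, and the statistical paragraph assigns them to correlations with improvement. They make up 1 + 4 + 8 = 13 of the 21 measures. This stands too, and it is why the four-component figures belong beside the larger ones. It does not remove the gap, because all outcomes are assessed after both arms and muscle characteristics are named in the negative condition itself.

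A reader might also use the chance of any significant result in either direction, 43-47% at ρ = 0.5. A significant worsening does not rescue the AFO, so that is not the relevant rate.

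Finally, a cautious condition for abandoning a device is defensible with 30 patients. This stands, and it limits what the fix should do.

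**Conclusion.** The point holds as a gap in the Aim 2 analysis and interpretation text. The planned multiplicity allowance is not carried into the analysis, the remaining outcomes have no stated status, and the negative conclusion is not linked to the named main comparison.

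The size depends on what *components* means: 6-10% for the four named components, and 11-47% for the 21-25 listed measures (22-23% at ρ = 0.5), against 2.5% for one test. These figures rest on two-sided 0.05 for each comparison, an assumed common correlation between 0 and 0.8, and no true effect on any measure.

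The stronger reading, that the plan would declare a useless AFO effective on any one significant measure, is not supported. Avoiding the negative conclusion is not a claim of benefit, and the scenarios that do claim benefit require several domains to improve together.

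**What to change.** In Specific Aim 2, Statistical analysis, state that the efficacy claim rests on the AFO-minus-control contrasts in initial and absolute walking distance, each tested at the planned two-sided 0.025. Label all other activity, quality-of-life, oxygenation, thickness, strength and gait comparisons exploratory, reported with estimates and confidence intervals.

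In Specific Aim 2, Expected results/possible limitations, add that an isolated significant exploratory measure does not by itself count as a component of the hypothesis being correct. Do not make a non-significant walking distance alone the ground for abandoning the AFO, for the reason in step 5.

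The cost is a few sentences, with no new data or patients. Each walking distance is tested at 0.025 instead of 0.05, so power at 0.59 SD is the planned 80% and not 88%. An isolated activity, quality-of-life or muscle result can no longer support a claim of benefit.
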